1.3.2. Pharmacokinetics

The summary of information is based on data generated from studies conducted using a reference pirtobrutinib tablet. As of September 30, 2020, PK data were available from 181 patients enrolled in the LOXO-BTK-18001 study. Steady-state PK parameters of

pirtobrutinib in these cancer patients could be derived from data collected on Cycle 1 Day 8 (Figure 1), and are shown in Table 3. These data show that pirtobrutinib is absorbed after oral administration with a median time to maximum observed plasma concentration (t_{max}) of approximately 2 hours and low clearance (Table 3). Due to the limited sampling interval (0 to 8 hours), imputation for the 24-hour sample was made from Cycle 1 Day 8 predose sample, leading to an estimated plasma half-life of approximately 20 hours. Maximum observed plasma concentration and area under the plasma concentration-time curve (AUC) of pirtobrutinib showed an increase proportional to dose (Figure 2). Following administration of the recommended Phase 2 dose 200 mg QD, mean trough plasma levels of pirtobrutinib exceeded the concentration required for 96% inhibition of BTK in vitro ($IC_{50} = \text{CCI}$
 $IC_{96} = \text{CCI}$). Further details may be found in the IB.¹

Pharmacokinetic data following oral administration of a 200-mg dose of pirtobrutinib in tablet form in healthy volunteers in the LOXO-BTK-20014 study indicate that there was little effect of either a standard meal or the proton pump inhibitor (omeprazole) on the PK of pirtobrutinib.

**Table 3: Pharmacokinetic Parameters of Pirtobrutinib in Cancer Patients
(Study LOXO-BTK-18001) at Steady State (Cycle 1 Day 8)**

Dose Level		max	max	0-8	0-24			Ratio AUC ₀₋₈ Day
25 mg QD								
50 mg QD								
100 mg QD								
150 mg QD								
200 mg QD								
250 mg QD								
300 mg QD								

Abbreviations:

AUC₀₋₂₄ = area

C_{max} = maximum

of subjects; QD = once daily; t_{1/2} = half-life; t_{max} = time of maximal plasma concentration.

^a N = 4, ^b N = 5, ^c N = 8, ^d N = 18, ^e N = 64, ^f N = 21, ^g N = 16, ^h N = 73

SDTM Transfer: September 30, 2020

CCI

CCI

optimization of the commercial site process, differences in the dissolution profiles were identified. Therefore, this study is designed to compare the PK of T2 tablets manufactured at the clinical trial site (reference [R]) and T2 tablets manufactured at the commercial site (test [T]) in healthy subjects.

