8. SAMPLE SIZE AND DATA ANALYSIS

8.1. Determination of Sample Size

Up to 28 healthy adult male and female subjects (women of non-childbearing potential only) will be enrolled. This is a relative bioavailability study; however, a total of 28 evaluable subjects (14 subjects per treatment sequence) will provide at least 81% power to have the respective 90% confidence intervals (CIs) for the geometric mean ratios for C_{max} and AUC values between test and reference lot tablets are within the interval of 80.00% to 125.00%,

assuming a within subject coefficient of variation (CV) of 25% and that the expected ratio of means is 1.05 (or 0.95). Based on PK results of LOXO-BTK-20009, CV% of AUC is around 25%. Replacement subjects may be enrolled only if deemed necessary by the Sponsor. Every attempt will be made to enroll at least 3 subjects of each sex in the study.

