8.3. Pharmacokinetic Analysis

Serial PK blood samples for the analysis of plasma concentrations of pirtobrutinib and for future potential and/or exploratory analysis will be collected from predose through 168 hours postdose for each treatment. Whenever possible, the following PK parameters will be calculated for each subject, based on the plasma concentrations of pirtobrutinib (as appropriate):

- AUC_{0-24}
- AUC_{0-t}
- AUC_{0-inf}
- % AUC_{extrap}
- CL/F
- $t_{1/2}$
- C_{max}
- t_{max}
- λ_z
- V_z/F .

Pharmacokinetic calculations will be performed using commercial software such as Phoenix™ WinNonlin® Version 8.1 or higher (Certara USA Inc.).

Other parameters may be added as appropriate. Final PK parameters reported will be detailed in the statistical analysis plan (SAP).

Pharmacokinetic analysis will use actual times as recorded on the eCRF. All statistical analyses will be performed using SAS® Version 9.4 or greater. More details on the analyses will be included in the SAP.

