5. SAMPLE SIZE JUSTIFICATION

Up to 28 healthy adult male and female subjects (women of non-childbearing potential only) will be enrolled. This is a relative bioavailability study; however, a total of 28 evaluable subjects (14 subjects per treatment sequence) will provide at least CCI power to have the respective 90% confidence intervals (CIs) for the geometric mean ratios for C_{max} and AUC values between test and reference lot tablets are within the interval of 80.00% to 125.00%, assuming a CCI and that the expected ratio of means is 1.05 (or 0.95). Based on PK results of LOXO-BTK-20009, CCI

■ Replacement subjects may be enrolled only if deemed necessary by the Sponsor. Every attempt will be made to enroll at least 3 subjects of each sex in the study.

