8.5.1.2. Criteria for Calculation and Reporting of Area Under the Concentration-time Curve

The minimum requirement for the calculation of AUC will be the inclusion of at least 3 consecutive concentrations above the lower limit of quantification. If there are only 3 consecutive concentrations, at least 1 should follow C_{max} .

The AUC_{0-inf} values where the percentage extrapolation is less than 30% will be reported. The AUC_{0-inf} values where the percentage extrapolation is greater than 30% will be listed but excluded from descriptive statistics.

If $AUC_{0-\infty}$ cannot be determined reliably for all subjects and/or treatments, an alternative AUC measure, such as AUC to a fixed timepoint or AUC_{0-t} , may be used in the statistical comparison of treatments.

8.5.1.3. Criteria for Handling Concentration Below the Limit of Quantification or Missing Concentrations for Pharmacokinetic Analysis

Plasma concentrations below the limit of quantification (BLQ) will be assigned a value of 0 before the first measurable concentration and thereafter BLQ concentrations will be treated as missing. The following rules apply to the specific situations defined below:

- If an entire concentration-time profile is BLQ, it will be excluded from PK analysis.
- Where 2 or more consecutive concentrations are BLQ at the end of a profile, the profile will be deemed to have terminated and any further quantifiable concentrations will be set to missing for the calculation of the PK parameters, unless they are considered to be a true characteristic of the profile of the drug.
- If a predose plasma concentration is missing, it will be set to 0 by default within Phoenix WinNonlin.

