8.5.3. Pharmacokinetic Statistical Methodology

A statistical analysis will be conducted to investigate the relative bioavailability of 200 mg pirtobrutinib test lot tablets (test treatment) versus 200 mg pirtobrutinib reference lot tablets (reference treatment).

The hypothesis testing will be 2-sided and carried out on 0.1 significance level.

The natural log (ln)-transformed⁴ AUC_{0-t} , AUC_{0-inf} , and C_{max} (only for plasma pirtobrutinib) will be analyzed using a mixed model.⁵ The model will include planned treatment sequence, period, and actual treatment as fixed effects, and subject within planned treatment sequence as a random effect.

For each PK parameter separately, the least squares mean (LSM) for each treatment, difference in LSMs between the test and reference treatments, and corresponding 90% CI will be calculated; these values will then be back-transformed to give the geometric least square mean (GLSM), geometric mean ratio (GMR), and corresponding 90% CI.

It will be concluded that the test treatment is bioequivalent to the reference treatment if, for all tested PK parameters, the 90% CI for GMR is completely contained within the predefined interval of (80.00%, 125.00%).⁶ This procedure is equivalent to Schuirmann's⁷ two one-sided tests at the 0.05 level of significance.

Additionally, the pooled estimate (across treatments) of the within-subject CV will be calculated, and residual plots will be produced to assess the adequacy of the model(s) fitted.

Examples of the SAS code that will be used are as follows:

Mixed Model Analysis

```
proc mixed data = <data in>;
```

```
by parcat1n parcat1 pkday paramn param;
class trtan aperiod trtseqp usubjid;
model lpk = trtan aperiod trtseqp / cl residual ddfm = kr;
lsmeans trtan / cl pdiff = control('1') alpha = 0.1;
random intercept / subject = usubjid(trtseqp);
ods output lsmeans = <data out>;
ods output diffs = <data out>;
ods output covparms = <data out>;
run;
```

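### The 81% power in Protocol 8.1 is for one PK parameter at a time; power for the SAP 8.5.3 rule that every tested parameter must pass is lower and is not stated

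*Protocol*

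**What the plan says.** Protocol 8.1 plans for "a total of 28 evaluable subjects (14 subjects per treatment sequence") and states that this number "will provide at least 81% power to have the respective 90% confidence intervals (CIs) for the geometric mean ratios for C_{max} and AUC values" to lie within 80.00% to 125.00%. One CV (25%) and one true ratio (1.05 or 0.95) serve for both Cmax and AUC. The only source given for the CV is an AUC figure: "Based on PK results of LOXO-BTK-20009, CV% of AUC is around 25"%. Nothing comparable is cited for Cmax, and no correlation between parameters is mentioned.

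SAP 8.5.3 fits a separate model to each of ln AUC0-t, ln AUC0-inf and ln Cmax, then declares the test lot bioequivalent "if, for all tested PK parameters, the 90% CI for GMR is completely contained within the predefined interval" of 80.00% to 125.00%. SAP 8.5.1.2 adds that if AUC0-inf "cannot be determined reliably for all subjects and/or treatments, an alternative AUC measure" may be used for the comparison.

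SAP 5 repeats the sample size sentence with the power and the CV blacked out ("will provide at least CCI power to have the respective 90% confidence intervals (CIs")). What follows therefore rests on the protocol's figure.

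**The concern.** The protocol attaches one power figure to a statement about both Cmax and AUC. The SAP's conclusion requires all three intervals to fall inside the limits. The probability that several conditions all hold cannot exceed the probability of any one of them. It equals that probability only if the others never fail when that one holds, which with a common CV and ratio means perfect correlation. If 81% is a one-parameter figure, the trial's chance of reaching its planned conclusion is therefore lower than a reader would take from Protocol 8.1.

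The stake is how the result is read. If one parameter narrowly misses, the miss will be judged against a stated failure risk of about 19%, when the risk under the plan's own assumptions was higher.

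**Working it through.** **Inputs from the documents.** N = 28, 14 per sequence, 2×2 crossover, so 26 residual degrees of freedom; CV 25%; true ratio 1.05 or 0.95; limits 0.80 and 1.25 (Protocol 8.1). Two one-sided tests at 0.05, equivalent to the 90% CI; all of AUC0-t, AUC0-inf and Cmax must pass (SAP 8.5.3).

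**Step 1: reproduce the 81%.**

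- Log-scale within-subject SD: √ln(1 + 0.25²) = √0.0606 = 0.2462.
- Standard error of the treatment difference: 0.2462 × √(2/28) = 0.0658.
- Critical value t(0.95, 26) = 1.706; limits ±ln 1.25 = ±0.2231; ln 1.05 = 0.0488; ln 0.95 = −0.0513.
- With μ the log of the true ratio, X a chi-square variable on 26 df and h = 1.706 × 0.0658 × √(X/26), power is the average over X of Φ((0.2231 − h − μ)/0.0658) − Φ((−0.2231 + h − μ)/0.0658), taken as zero when negative.

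This gives 81.6% at 1.05 and at 1/1.05, 80.7% at 0.95, and 90.2% at 1.00. The protocol's 81% is thus a one-parameter power. At a literal 0.95 it holds only after rounding, which is not a separate fault.

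**Step 2: what to assume about correlation.** The documents give no correlations, so these are assumptions.

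- *AUC0-t with AUC0-inf.* Protocol 1.3.2 reports data "leading to an estimated plasma half-life of approximately 20 hours" (patients, with an imputed 24-hour sample). Protocol 8.3 says samples "will be collected from predose through 168 hours postdose for each treatment". That is 168/20 = 8.4 half-lives. If decline is mono-exponential and concentrations stay quantifiable, the fraction of exposure left after 168 hours is 0.5^8.4 = 0.3%. The two AUCs should nearly coincide; 0.98 and 0.999 are used.
- *AUC with Cmax.* Taken from 0 to 0.95.

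**Step 3: joint power.** Simulation with 400,000 trials per setting, using correlated normal estimates and correlated residual variances, with CV 25% and the same true ratio for every parameter:

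| Rule | True ratio | AUC-Cmax 0 | 0.5 | 0.7 | 0.9 | 0.95 |
|---|---|---|---|---|---|---|
| Three parameters, AUC-AUC 0.98 | 1.05 | 65% | 69% | 71% | 75% | 77% |
| Three parameters, AUC-AUC 0.98 | 0.95 | 63% | 68% | 70% | 74% | 76% |
| Three parameters, AUC-AUC 0.999 | 1.05 | 66% | 70% | 72% | 76% | 78% |
| Three parameters, AUC-AUC 0.999 | 0.95 | 65% | 69% | 71% | 75% | 77% |
| One AUC and Cmax only | 1.05 | 67% | 70% | 73% | 76% | 78% |

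As a check, two independent parameters at 1.05 give 0.8163² = 66.6%, which agrees with the last row. Even at AUC-Cmax 0.99 and AUC-AUC 0.999, the three-parameter rule gives 79.8% at 1.05.

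The last row shows that most of the loss comes from needing both an AUC and Cmax to pass. Replacing AUC0-inf with another AUC measure under SAP 8.5.1.2 does not remove it.

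**Step 4: departures from the stated inputs.** All are assumed, with AUC-AUC 0.98 and AUC-Cmax from 0 to 0.95:

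| Case | Joint power |
|---|---|
| All true ratios 1.00, CV 25% | 80-87% |
| AUC CV 20%, Cmax CV 25%, ratio 1.05 | 76-82% |
| Cmax CV 20%, AUC CV 25%, ratio 1.05 | 75-79% |
| AUC ratio 1.00, Cmax ratio 1.05, CV 25% | 72-77% |
| Cmax CV 30%, AUC CV 25%, ratio 1.05 | 52-65% |

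**The case against.** The strongest reply is that the sentence is not false. It speaks of the respective intervals, SAP 8.5.3 analyses each parameter separately, and 81% is right on that reading. What is missing is then a supplementary figure. That reading is available, but the sentence does not say the power is per parameter. Even if it did, the power for the conclusion the SAP plans to draw would still be absent.

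Second, the objective is relative bioavailability, and Protocol 8.3.2 plans ratios and 90% CIs with no pass/fail rule. This stands, and it limits the reach of the point: the estimates answer the objective whatever the joint power. But Protocol 8.1 itself justifies the sample size by the 80.00% to 125.00% criterion, and SAP 8.5.3 writes a formal bioequivalence conclusion on it.

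Third, the size of the gap depends on quantities the documents do not give. Cmax and AUC come from the same concentration profile, so zero correlation is better read as a bound than as an expected case. With AUC-Cmax correlation of 0.7 to 0.95, joint power at 1.05 is about 71-78%, a shortfall of roughly 4 to 10 points. If one CV is below 25%, or the true ratios are closer to 1, the gap can shrink or vanish; a larger Cmax CV widens it. All of this is fair and is why the answer is a range. It does not change the direction at the plan's own common CV and ratio.

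**Conclusion.** The point holds. Protocol 8.1's 81% is the power for one parameter. For the all-parameters rule in SAP 8.5.3, at the same CV and ratio, power is about 65-78% at 1.05 and 63-77% at 0.95, so the planned conclusion would be missed roughly 22-37% of the time. These ranges assume 28 evaluable subjects, CV 25% for all three parameters, an AUC0-t/AUC0-inf correlation of 0.98 to 0.999 and an AUC-Cmax correlation of 0 to 0.95. That joint power is lower does not depend on the particular correlation, short of near-perfect; how much lower does.

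Requiring every parameter to pass does not inflate type I error. This is a figure to restate, not a flaw in the design or analysis. If the redacted part of SAP 5 already gives a joint power, only the protocol text needs attention.

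**What to change.** In Protocol 8.1, and in SAP 5 if its redacted figure is the same, describe the figure as about 81% power for each PK parameter separately. Add one sentence giving the joint power for the rule in SAP 8.5.3, with the CVs, ratios and correlations it assumes. The best inputs are the within-subject CVs of AUC and Cmax, and their correlation, from LOXO-BTK-20009. If those are not available, give a labelled range: for example, roughly 65-78% at a ratio of 1.05, with CV 25% throughout, AUC-AUC correlation of 0.98 or more and AUC-Cmax correlation of 0 to 0.95, noting that zero is a bound.

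The cost is two sentences and a less favourable stated power. Changing the protocol text needs sponsor and investigator agreement under Protocol 9.1. Since the SAP supersedes the protocol's statistical considerations (SAP 1), a statement in the SAP would serve if a protocol change is not wanted. Sample size, model and decision rule stay as they are.

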8.2. Analysis Populations

8.2.1. Pharmacokinetic Population

The PK population will include all subjects who have received a dose of study drug, have at least 1 quantifiable plasma concentration, and for whom at least 1 PK parameter can be computed. A subject may be excluded from the PK summary statistics and statistical analysis if the subject has an AE of vomiting that occurs on or before t_{max} . The impact of protocol deviations on the PK population will be evaluated on a case-by-case basis.

8.2.2. Safety Population

The safety population will consist of all subjects who have received at least 1 dose of study drug. Subjects will be classified into groups based on actual treatment received.

8.3. Pharmacokinetic Analysis

Serial PK blood samples for the analysis of plasma concentrations of pirtobrutinib and for future potential and/or exploratory analysis will be collected from predose through 168 hours postdose for each treatment. Whenever possible, the following PK parameters will be calculated for each subject, based on the plasma concentrations of pirtobrutinib (as appropriate):

- AUC_{0-24}
- AUC_{0-t}
- AUC_{0-inf}
- % AUC_{extrap}
- CL/F
- $t_{1/2}$
- C_{max}
- t_{max}
- λ_z
- V_z/F .

Pharmacokinetic calculations will be performed using commercial software such as Phoenix™ WinNonlin® Version 8.1 or higher (Certara USA Inc.).

Other parameters may be added as appropriate. Final PK parameters reported will be detailed in the statistical analysis plan (SAP).

Pharmacokinetic analysis will use actual times as recorded on the eCRF. All statistical analyses will be performed using SAS® Version 9.4 or greater. More details on the analyses will be included in the SAP.

8.3.1. Descriptive Analysis

Plasma concentrations and PK parameters will be summarized with descriptive statistics (number, arithmetic mean, standard deviation, CV%, geometric mean, geometric CV%, median, minimum, and maximum) by treatment.

Individual and mean plasma concentration-time curves (both linear and log linear) will be included in the final report.

8.3.2. Statistical Methodology

The primary PK analysis planned for this study is a mixed effect model including planned treatment sequence, period, and actual treatment as fixed effects and subject within planned treatment sequence as a random effect will be used to analyze the natural log-transformed PK parameters (AUC_{0-t}, AUC_{0-inf}, and C_{max}) and will include calculation of least squared (LS) means and the difference between treatment LS means, as well as their corresponding 90% CIs. The geometric mean ratios and their 90% CIs of the PK parameter for each treatment comparison will be constructed using the exponentiation of the difference and the CIs from the mixed effect model. The comparison of interest is Treatment T (as test) compared with Treatment R (as reference).

8.4. Safety Analysis

All safety assessments, including AEs, SAEs, vital sign measurements, clinical laboratory results, physical examination results, concomitant medications, and 12-lead ECGs, will be tabulated and summarized where possible, using descriptive methodology, as needed, by timepoint. Unless otherwise specified, baseline value is defined as the last non-missing measurement before administration of study drug for each period (ie, Day 1 and Day 8). No formal statistical analyses are planned for the safety data. All safety data will be listed by subject.

Concomitant medications will be coded using the World Health Organization (WHO) Drug Dictionary (WHO Drug Global B3, September 2019). Adverse events will be coded using Medical Dictionary for Regulatory Activities Version 22.1 (or higher). The incidence of AEs will be presented by severity and by relationship to study drug as determined by the Investigator or designee ([Appendix 1](#) for AE reporting). All TEAEs will be summarized by system organ class and preferred term.

8.5. Data Handling and Record Keeping

Any changes to information in the trial progress notes and other source documents will be initialed and dated on the day the change is made by a CRU staff member authorized to make the change. Changes will be made by striking a single line through erroneous data and clearly entering the correct data (eg, ~~wrong data~~ right data). If the reason for the change is not

apparent, a brief explanation for the change will be written adjacent to the change by the CRU staff member.

The Data Management Plan will be approved by the Sponsor.

Data will be validated during data entry by the CRU and verified by the Study Monitor. Data will then be reviewed by the data management group to resolve any outstanding issues. Listings will be generated after the database is cleaned by data management and will be reviewed by the Labcorp Drug Development scientific team. The eCRF and ancillary data will be converted into final SAS® datasets following Study Data Tabulation Model or Sponsor-provided specifications. The final datasets structure will be verified using Web Submission Data Manager®, while the dataset content will be peer reviewed by an independent programmer.

The tables, figures, and listings (TFLs) will be programmed per the final SAP. All TFLs will be peer reviewed by an independent programmer. In addition, draft TFLs will be reviewed by the Labcorp Drug Development scientific team during the dry run and data review meetings.

The peer review will be performed by independent programmers following the quality control process and programming checklists.

8.6. Quality Control and Quality Assurance

Quality control and quality assurance will be performed according to Labcorp Drug Development SOPs or per Sponsor request, and as applicable, according to the contract between Labcorp Drug Development and the Sponsor.

9. ADMINISTRATIVE ASPECTS

9.1. Change in Protocol

There will be no alterations in the protocol without agreement between the Sponsor and the Investigator (or designee).

There will be no alterations in the protocol affecting subject safety without the express written approval of the Sponsor, Investigator (or designee), and the IRB (see Form FDA 1572).

9.2. Site Initiation Visit/Investigator Meeting

Prior to the start of the clinical study, the representative(s) of the Sponsor and/or Sponsor will meet with the Investigator (or designee) and appropriate CRU staff to familiarize the Investigator (or designee) and CRU staff with the materials necessary for conducting the clinical study.

9.3. Disclosure

All information provided regarding the study, as well as all information collected/documentated during the study, will be regarded as confidential. The Investigator (or designee) agrees not to disclose such information in any way without prior written permission from the Sponsor.

Any publication of the results, in part or in total (eg, articles in journals or newspapers, oral presentations, abstracts) by the Investigator (or designee) or their representative(s), shall require prior notification and review, within a reasonable timeframe, by the Sponsor, and cannot be made in violation of the Sponsor's confidentiality restrictions or to the detriment of the Sponsor's intellectual property rights.

